7.4.4 Post-Treatment (SVR12) (V6) Visit

The following procedures will occur at the Post-Treatment (SVR12) visit (V6), which should be scheduled 12 weeks ± 4 days from the last dose of study medication. The V6 visit can occur simultaneously with the 8-week Follow-up Visit for the infant (iV1), as applicable. This is the last scheduled clinic visit specifically for the mother. If an HCV RNA test is not obtained at the V6 visit or abstracted from the medical record

^{**}Laboratory test performed as applicable for participants who deliver at site hospitals.

within the V6 visit window or later, then the participant is NOT evaluable and will be replaced with a new participant.

Table 8: Post Treatment (V6)

Visit 7 (V6) Post Treatment Visit		
Component Procedures		
Administrative and Regulatory	 Review/update locator information Visit questionnaire Provide reimbursement 	
Clinical	 Review/update medical history Review/update concomitant medications Perform modified physical examination Record/update AEs Provide available test results from delivery, as applicable 	
Laboratory	 Collect blood: CBC with platelets and differential Hepatic function panel (AST, ALT, albumin, total and direct bilirubin, alkaline phosphatase) PT/INR Creatinine/eGFR Lipase Creatine kinase HCV RNA viral load* Blood sample for HCV genomic deep sequencing (collected and only used in the case of treatment failure) or stored sample for future use, as applicable. 	

^{*}If the participant does not come to the V6 visit, then the HCV RNA viral load may be abstracted from the medical record if it occurs during the visit window or later. If the HCV RNA is detectable then every effort should be made to have the participant return for a blood sample for HCV genomic deep sequencing.

7.4.5 Infant Follow-Up Visits (iV1, iV2, iV3)

After delivery, infants will be seen at the following time points:

iV1: 8 weeks ± 6 weeks iV2: 6 months ± 1 month iV3: 12 months ± 1 month

The following procedures will occur at the Infant Follow-Up Visits (iV1, iV2, iV3). If blood sampling is not possible, then the results can be collected from the infant's medical record if available. Results of physical and developmental exams will be shared with the mother, and if necessary, with the infant's routine healthcare

provider. Referrals, for instance for early intervention, will be made as indicated by pediatric study staff.

Table 9: Infant Follow-Up Visits (iV1, iV2, iV3)

Visit iV1, iV2, iV3 Infant Follow-Up Visits			
Component	Component Procedures		
Administrative and Regulatory	 Review/update mother/guardian locator information Review infant demographics (iV1) Sign release(s) for medical records for infant, as applicable Provide reimbursement Schedule next visit (iV2, iV3) Review schedule of infant follow-up visits Protocol adherence counseling 		
Clinical	 Review/update medical history* Document pre-existing conditions (iV1)* Review/update concomitant medications* Record/update AEs Age-appropriate physical examination by pediatrician or designee, including growth assessment (weight, length, and head circumference)*** Developmental Exam (Ages and Stages Questionnaire®); with referrals as indicated Provide available laboratory test results, as applicable 		
Laboratory	 Collect infant blood HCV RNA (iV1, iV2, iV3) HCV genomic deep sequencing (only if HCV RNA is detectable)** 		

^{*}May be collected from the medical record as applicable

7.5 Follow-up Procedures for Participants Who Permanently Discontinue Study Medication

Participants will be permanently discontinued from study medication for significant laboratory abnormalities or adverse events as outlined in section 9.3 and 9.4, or if they choose to discontinue study medication. The participant will be asked to continue in the study and complete applicable remaining study procedures for safety purposes, including maternal and infant study procedures. To reduce burden on the participant and prevent lost to follow-up, in person visits can be converted to telephone visits for the collection of adverse events and safety labs can be collected from the medical record as performed for standard of care.

Participants who are permanently discontinued from study medication will be instructed to return any remaining study medication. All protocol-specified study procedures will continue for safety except the following:

- Provision of study medication
- Provision of medication use/adherence counseling

The following procedures will be performed at the visit at which study medication use is permanently discontinued or at the next in person visit:

^{**}If HCV RNA is detectable at iV1, iV2 or iV3, then HCV genomic deep sequencing should be collected/stored. If infant is at high-risk of HCV perinatal transmission, then an additional sample can be drawn at the time of the HCV RNA test and stored until the HCV RNA test has resulted. If the HCV RNA result is undetectable, then the stored sample will be discarded.

^{***}An age-appropriate physical exam is required during the infant study visit. However, if the infant participant misses a visit, then an age-appropriate physical exam may be abstracted from the medical records if it occurs during the visit window.

- HCV viral load
- HCV genomic deep sequencing (collected and used as necessary) or stored sample for future use, as applicable
- Medical history review
- Concomitant medication review
- Record/update AEs
- Modified physical examination including vital signs, if indicated.

If an in person visit is not possible, applicable information may be retrieved from their routine care medical chart as appropriate.

7.5.1 Interim Visits

Interim visits may be performed at any time during the study. Study procedures may be repeated at interim visits as clinically indicated. All interim contacts and visits will be documented in participants' study records and on applicable eCRFs.

7.6 Adherence Counseling and Assessment

Adherence counseling regarding the study protocol will be performed at each applicable study visit. Additionally, investigators may use text messaging, follow-up phone calls, email, and/or meeting study participants at their regular clinic visits in order to improve adherence to study medication and procedures. At the follow-up visits (V3 and V4), all unused medication will be counted, recorded and returned to the study staff and handled according to the site SOP. Participants will receive written instructions on how and when to take the medication and directions on how to store the medication as well as what to do if the medication is lost or stolen. Research staff will recommend that participants take the study medication consistently at a time convenient for their schedule. If a participant forgets to take a dose, she should take the missed dose as soon as she remembers but should not take more than one tablet of SOF/VEL per day (24-hour period).

7.7 Clinical Evaluations and Procedures

Maternal

Physical exams will include the following assessments:

- General appearance
- Height[^] and Weight
- Vital signs: temperature, pulse, blood pressure, respirations
- Fundal height (if gestational age > 20 weeks)
- Abdomen*
- Head, Eye, Ear, Nose and Throat (HEENT)*
- Lymph nodes*
- Neck*
- Heart*
- Lunas*

- Extremities*
- Skin*
- Neurological*
- · Symptom-directed examination at all follow-up visits
- Fetal Heart Tones**
 - ^obtained at Screening Visit only
 - *obtained at Screening Visit and prn
 - **Performed for mother at screening, enrollment, V3, V4, V5, and prn)

Infant

- Age-appropriate physical exam
- Weight, length, head circumference
- Ages and Stages Questionnaire® (iV1, iV2, iV3)

7.8 Laboratory Evaluations

Site clinical laboratory

- Maternal Blood
 - Hepatitis B virus testing (HBsAg, anti-HBc, anti-HBs) if not done as part of routine prenatal testing
 - HCV RNA viral load
 - o Hepatitis C genotype, as applicable
 - CBC with differential and platelets
 - Creatinine/eGFR
 - Hepatic function panel: AST, ALT, albumin, total and direct bilirubin, alkaline phosphatase
 - PT/INR
 - Lipase
 - Creatine kinase
 - HIV viral load and CD4 count, as part of screening/eligibility as needed
- Infant Blood
 - HCV RNA viral load

[name]

- Maternal blood and infant blood
 - Next Generation Sequencing (prn) OR if maternal sample not used for sequencing, it may be used for future use at the study site of collection if participant agrees

7.9 Specimen Collection and Processing

The study site will adhere to the standards of good clinical laboratory practice and local standards for proper collection, processing, labeling, transport, and storage of specimens.

7.10 Biohazard Containment

As the transmission of hepatitis C and other blood-borne pathogens can occur through contact with contaminated needles, blood and other bodily fluids, appropriate blood and secretion precautions will be employed by all personnel during blood draws and processing and handling of all specimens for this study as recommended by the CDC and National Institutes of Health (NIH). Biohazardous waste will be contained according to institutional, transportation/carrier, and all other applicable regulations.

8 ASSESSMENT OF SAFETY

8.1 Safety Monitoring

Site study investigators are responsible for the evaluation, documentation and reporting of all adverse events, for continuous close safety monitoring of all study participants and for alerting the Protocol Safety Review Team (PSRT) if any unexpected concerns arise. The PSRT will be comprised of, at the minimum, the following: protocol chair, the site PIs, an independent safety physician, a pediatric co-Investigator, data management statistician, and a Gilead Sciences representative. The data management team at the data coordinating center will prepare routine AE and clinical data reports for review by the PSRT monthly and will meet in person or via conference call approximately every three months or as needed throughout the study period to review safety data, discuss product management, and to address any potential safety concerns.

Evaluation of safety concerns will be conducted at the site as clinically indicated. All adverse events will be documented and followed to their resolution or until clinically stable. Site investigators are responsible for notifying the Protocol Chair and PSRT if unexpected and/or serious adverse events occur. The Protocol Chair will notify Gilead Sciences, as applicable. Each site is responsible for reporting adverse events to their own local IRB/REB as required by their local guidelines.

8.2 Clinical Data and Safety Review

A multi-tiered safety review process will be followed for the duration of this study. The site investigators are the first layer of this tiered system and are responsible for the initial evaluation and reporting of safety information at the participant level, and for alerting the Protocol Chair and PSRT if any unexpected safety concerns arise.

Participant safety is also monitored at the data coordinating center level through a series of routine reviews conducted by the data management team as well as the PSRT. The data management team at the coordinating center will review incoming safety data on an ongoing basis. Events identified as questionable, inconsistent, or unexplained will be queried for verification. The PSRT will review clinical data reports on a monthly basis, beginning at approximately one month from the first

enrollment. In addition to the monthly safety data reviews, the PSRT will convene on an approximate quarterly basis to review the AE report and on an ad hoc basis to make decisions regarding the handling of any significant safety concerns. If necessary, external experts representing expertise in the fields of obstetrics, neonatology, infectious diseases, hepatology, statistics and medical ethics may be invited to join the safety review. A recommendation to pause or stop the trial may be made at this time or at any such time that the safety review team agrees that an unacceptable type and/or frequency of AEs has been observed.

8.3 Adverse Events Definitions and Reporting Requirements

8.3.1 Adverse Events

An AE is defined as any untoward medical occurrence in a clinical research participant administered an investigational medication and which does not necessarily have a causal relationship with the investigational medication. As such, an AE can be an unfavorable or unintended sign (including an abnormal laboratory finding, for example), symptom or disease temporally associated with the use of an investigational medication, whether or not considered related to the medication. The term "investigational medication" for this study refers to the study medication. This definition of an adverse event is applied to all study participants from the time of enrollment, which is the time the participants begin taking the study medication.

Study participants will be provided instructions for contacting the study site to report any untoward medical occurrences they may experience throughout their participation in the study. They will be instructed to seek medical care with their local primary care physician/obstetrical team, as necessary. Participants may have an unscheduled visit with the site PI/study clinicians as necessary or desired in applicable circumstances. In cases of potentially life-threatening events, participants will be instructed to seek immediate emergency care. With appropriate permission of the participant, whenever possible, records from all non-study medical providers related to untoward medical occurrences will be requested and required data elements will be abstracted and recorded on study CRFs. All participants reporting an untoward medical occurrence will be followed clinically as deemed appropriate by a site PI/designee until the occurrence resolves (returns to baseline) or stabilizes. Study site staff will document AEs reported by or observed in enrolled study participants by severity and presumed relationship to investigational medication, including gradable laboratory findings. AE severity and laboratory tests will be graded per the most recent version of the DAIDS Table for Grading the Severity of Adult and Pediatric Adverse Events.

Certain adverse events are expected as a consequence of pregnancy as well as labor and delivery. These events may be found in the Clinical Management SSP. In addition, the Clinical Management SSP will also provide guidance for adverse event grading for pregnancy-associated adverse events that occur during pregnancy, such as bleeding, pregnancy induced hypertension, chorioamnionitis. This SSP will also provide guidance adverse event reporting for infants that were exposed to opioids.

For any serious adverse events (SAEs) that are continuing at a participant's study exit visit, the site PI/designee must establish a clinically appropriate follow-up plan for the AE. At a minimum, the SAE must be re-assessed by study staff 30 days after the participant's study exit visit; additional evaluations also may take place at the discretion of the site PI/designee. The same approach must be taken for any AEs that are found to have increased in severity at the study exit visit, or any new ≥ Grade 3 AEs uncovered at the last visit. For those AEs requiring re-assessment, if the AE has not resolved or stabilized at the time of re-assessment, study staff will continue to re-assess the participant at least once per month while the study is ongoing. After the study has ended, all AEs requiring re-assessment will be re-assessed at least once within the 30-60 days after the study end date. The PSRT may advise study staff as to whether any additional follow-up may be indicated on a case-by-case basis.

8.3.2 Serious Adverse Events

An SAE will be defined as an AE that:

- Results in death.
- Is life-threatening.
- Requires inpatient hospitalization or prolongation of existing hospitalization.
- Results in persistent or significant disability/incapacity.
- Is a congenital anomaly/birth defect.
- Is an important medical event that may not result in death, be immediately life-threatening, or require hospitalization but may jeopardize the participant or require intervention to prevent one of the outcomes listed in the definition above.

8.3.3 Adverse Event Relationship to Study Medication

Relatedness is an assessment made by the site PI/designee of whether or not the event is related to the study agent.

- Related: There is a reasonable possibility that the AE may be related to the study medication
- Not Related: There is not a reasonable possibility that the AE is related to the study medication

8.4 Adverse Event Reporting Requirements

8.4.1 Reporting Requirements for this Study

All adverse events will be reported to Gilead Sciences on a monthly basis by the Data Management Team. All serious adverse events that are considered unexpected and related to the study medication will be reported to the respective site Institutional Review Board as applicable and per local reporting guidelines, and

the FDA at the time of annual renewal or before if it meets FDA reporting requirements and will follow Health Canada reporting requirements. As such, during the course of the clinical trial, the sponsor will inform the Minister of any serious unexpected adverse drug reaction that has occurred within or outside Canada by i) 15 days of becoming aware of the information if neither fatal nor life threatening, and ii) within 7 days of becoming aware of the information if fatal or life threatening.

The site PI will notify the Protocol Chair and PSRT within 7 days of becoming aware of the SAE. The Protocol Chair will be responsible for notifying Gilead Sciences within 15 days of becoming aware of the event.

8.4.2 Grading Severity of Events

The most current Division of AIDS Table for Grading the Severity of Adult and Pediatric Adverse Events (DAIDS AE Grading Table) is available on the RSC website at http://rsc.tech-res.com/safetyandpharmacovigilance/.

8.5 Regulatory Requirements

Information on all applicable AEs will be included in reports to the FDA and Health Canada, and other applicable government and regulatory authorities. The site PI or designee will submit AE information in accordance with the requirements of the respective site IRB/REB.

8.6 Social Harms Reporting

Although every effort will be made to protect participant privacy and confidentiality, it is possible that participants' involvement in the study could become known to others and that social harms may result. Social harms that are judged by the study investigators to be serious or unexpected will be reported to the Protocol Chair and Gilead Sciences and to the respective site IRB/REB.

9 CLINICAL MANAGEMENT

Guidelines for clinical management and permanent discontinuation of study medication are outlined in this section. In addition, detailed information regarding specific adverse events can be found in the Clinical Management SSP. In general, the site PI/designee will only discontinue study medication in consultation with the Protocol Chair and independent safety physician if they feel that the risk of study medication continuation outweighs the benefits of study medication continuation. All permanent discontinuations will be documented on applicable CRFs.

9.1 Grading System

AE severity grading is described in Section 8.3.1.

9.2 Dose Modification Instructions

No dose modifications will be permitted in this study.

9.3 General Criteria for Permanent Discontinuation of Study Medication

A participant will be permanently discontinued from medication use by the site Pl/designee for any of the following reasons:

- Upon confirmation with a second result of a 5-fold or greater increase in ALT or AST at the V3 visit compared to baseline result (Screening visit) and must be greater that 3-fold higher than the upper limit of normal and cannot be attributed to another cause (such as cholestasis of pregnancy, preeclampsia, etc.).
- Any increase of ALT or AST above baseline (Screening visit) at the V3 visit that is accompanied by development of new ascites, jaundice (total bilirubin >3.0 mg/dL/51 µmol/L) or hepatic encephalopathy, that cannot be attributed to another cause.
- Upon confirmation with a second result of a 3-fold or greater increase in ALT or AST accompanied by direct bilirubin >2x the upper limit of normal that cannot be attributed by another cause.
- Participant is unable or unwilling to comply with required study procedures
- Participant might be put at undue risk to their safety and well-being by continuing medication use, according to the judgment of the study investigators.

The study investigators will consult with the PSRT prior to all study medication discontinuation. Both the independent safety physician and one of the hepatologist site principal investigators must review the case prior to stopping the medication.

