 - Perinatal term (>= 37 weeks) composite defined as fetal or neonatal death, respiratory support, Apgar score ≤ 3 at 5 minutes, hypoxic ischemic encephalopathy, seizure, infection (sepsis or pneumonia), birth trauma, meconium aspiration syndrome, intracranial or subgaleal hemorrhage, or hypotension requiring vasopressor support

- Admission to the neonatal intensive care unit
- Neonatal death
- Major malformations, defined as structural abnormalities with medical, surgical or cosmetic importance
- Weight, length, and head circumference at birth (by exam or chart review), 8 weeks, six months and 12 months
- Neurodevelopmental assessments at 6 months and 12 months by Ages & Stages Questionnaires®
- 3. Infant HCV RNA PCR viral load at 8 weeks, 6 months and 12 months

Table 1: Study Visit Schedule

	Maternal Study Visit	Gestational Age (Weeks + Days)/Timing [†]
V1	Screening	12+0 to 29+6
V2	Enrollment*	20+0 to 30+0
V3	Safety check/Med dispense	4 weeks ± 7 days after treatment start
V4	Safety check/Med dispense	8 weeks ± 7 days after treatment start
V5	End of Treatment	Within 7 days after last dose
	Delivery Visit [^]	
V6/iV	Post-treatment for SVR12	12 weeks ± 4 days after last dose
	Infant Study Visit	Infant Age
V6/iV	Infant Visit 1	8 weeks ± 6 weeks
iV2	Infant Visit 2	6 months ± 1 month
iV3	Infant Visit 3	12 months ± 1 month

[†]These are target windows. If the participant cannot be seen within these windows, she should be seen as soon as possible. A delayed visit will not be considered a protocol deviation.

Screening and Enrollment visits are separate visits and therefore should not occur on the same day.

Ideally, once a participant starts study medication (V2, Enrollment), study visits while on study medication should be scheduled 28 days apart or as close to 28 days as possible.

^{*}Start SOF/VEL and continue for 12 weeks (84 days)

[^]The Delivery Visit may occur before or after V5

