7.2 Visit 1- Screening (V1)

Potential participants will be encouraged to speak with their primary care/OB provider to determine whether to initiate HCV treatment during pregnancy before enrolling in the study.

Written informed consent will be obtained before any screening procedures are initiated. Screening can take place anytime within the screening gestational age window (12+0 to 29+6 weeks) with gestational age being determined by available clinical information and confirmed by ultrasound prior to enrollment. The screening visit questionnaire will include information about the diagnosis of HCV, any past or ongoing HCV risk factors, and any past HCV care or treatment. If an anatomy ultrasound has not been performed by the time of the screening visit, then it should be performed prior to enrollment as part of routine obstetric care. The study team may assist the participant in scheduling this ultrasound. Multiple visits may be needed to complete all required screening procedures as necessary.

The actual screening visit may occur anytime during the protocol defined screening window of 12+0 to 29+6 weeks. Routine clinical care laboratory values collected up to 4 weeks prior to the **date of the screening visit** may be used for screening purposes. In this case, any STORC screening required laboratory tests that were not done as part of clinical care within 4 weeks should be drawn at the time of the STORC Screening Visit. Any exclusionary laboratory values can be repeated at a later date within the screening window. If the repeated laboratory values meet inclusion criteria, then the participant can be enrolled. If there is concern that the participant's health status has changed between the screening and the enrollment visit or if the study investigators have concerns about the woman's health status, the screening laboratories can be repeated prior to enrollment.

Table 3: Screening Visit (V1)

Table 3: Screening Visit (V1)					
Visit 1- Screening Visit Component Procedures					
Component					
Administrative and Regulatory	 Assess eligibility Review and obtain written informed consent ICF Comprehension Assessment Assign participant ID (PTID) Sign appropriate medical record releases (i.e. to obtain records from prenatal care and outside records as necessary) Collect locator information Collect demographic information Visit questionnaire Provide reimbursement for study visit Schedule next visit 				

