Clinical	 Collect medical history & review and print medical/prenatal records including documentation of previous hepatitis C treatment, if applicable Review and obtain documentation of previous liver biopsy, liver imaging and/or noninvasive measures of fibrosis, if applicable Collect concomitant medications Perform full physical examination, including Fetal Heart Tones (FHTs) Confirm gestational dating (by available clinical information but must be confirmed by ultrasound prior to enrollment) 				
Local Laboratory Tests	 Collect blood: Complete blood count (CBC) with differential and platelets* HCV antibody and RNA viral load* HCV genotype (if not available) Hepatic function panel (AST, ALT, albumin, total and direct bilirubin, alkaline phosphatase)* Creatinine/eGFR * If living with HIV, perform HIV RNA PCR (viral load) if not done within 30 days of screening and CD4 cell count if not done within 6 months of screening*** Hepatitis B virus testing (HBsAg, anti-HBc, anti-HBs) if not done as part of routine prenatal care PT/INR* Lipase* Creatine kinase* 				

^{***}If greater than 30 days between screening and enrollment, HIV RNA PCR must be repeated/available and within eligibility criteria to enroll

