7.3 Visit 2- Enrollment (V2)

The following procedures will occur at the enrollment visit (V2). The visit questionnaire includes any changes in the participant's medical history and any new or ongoing HCV risk factors. During the enrollment visit the participant will be given instructions on taking the study medication.

^{*}Results of routine clinical care laboratory testing conducted within 4 weeks of screening visit date may be used towards the screening visit.

Table 4: Enrollment (V2)

Enrollment Visit 2 (V2)		
Component Procedures		
Administrative and Regulatory	 Confirm eligibility Review/update locator information Visit Questionnaire Provide counseling regarding protocol adherence Provide reimbursement for study visit Schedule next visit 	
Clinical	 Review/update medical history Review/update concomitant medications Document pre-existing conditions Perform modified physical examination, including FHTs 	
Study Medication	 Provide instructions regarding study medication/daily use Provide study medication and observe first dose (day 1) of medication in office 	
Local Laboratory Tests	 Collect blood: HCV RNA viral load Blood sample for HCV genomic deep sequencing (collected but only used in the case of treatment failure) or stored sample for future use, as applicable If living with HIV and more than 30 days between screening and enrollment, HIV RNA PCR must be repeated prior to enrollment (if a clinical HIV viral load within 30 days of enrollment is not available) 	

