APPENDIX I: SCHEDULE OF STUDY VISITS AND EVALUATIONS (Mother)

	SCR (V1)	ENR (V2)	Visits 3 & 4 (V3, V4)	End of Treatment (V5)	Delivery**	Post treatment (V6)
ADMINISTRATIVE AND REGULATORY						
Informed consent	Х					
Assess informed consent comprehension	Х					
Assignment of PTID	Х					
Locator information	Х	Х	Х	Х	Х	Х
Demographic information	Х					
Visit Questionnaire	Х	Х	Х	Х	Х	Х
Eligibility assessment	Х					
Eligibility confirmation		Χ				
Reimbursement	Х	Х	Х	Х	Х	Х
Record/ update AEs			Х	Х	Х	Х
Schedule next visit	Χ	Х	Х		Х	
Protocol adherence counseling		Х	Х	Х	Х	X
Medication use/adherence counseling		Х	Χ		*	
CLINICAL						
Medical history, review/obtain records	Х	Х	Х	Х	Х	Х
Concomitant medications	Χ	Х	Х	Х	X	X
Document pre-existing conditions	Χ	Х				
Physical examination	X(full)	X(modified)	X (modified)	X(modified)	+ (modified)	X (modified)
Fetal Heart Tones	Χ	X	Χ	X		
Provide available test results	Χ	X	Χ	Х	Х	X
Collect Pregnancy Outcomes/MR review					Х	
LABORATORY						
HCV RNA viral load	Х	Х	Х	Х	Х	Х
HCV Genotype	*					
HBV Testing	*					
CBC with diff and platelets	Χ		X (V3)			Х
Creatinine	Χ		X (V3)			X
Hepatic Function Panel	Χ		X (V3)			X
Lipase	Χ		X (V3)			Х
Creatine kinase	Χ		X (V3)			X
PT/INR	Χ		X (V3)			X
HIV Viral Load and CD4 count	#					
Blood Sample (future		Х	X (V3)	Х		Х
use/sequencing prn)			7 (٧٥)			^
STUDY MEDICATION						
Provision of Study Medication		Х	X		*	
Collect Remaining Study Medication				Χ		
*If indicated						

^{*}If indicated

⁺May be performed or obtained from medical record

^{**}May be performed during hospital admission for participants who deliver at an accessible facility or applicable procedures conducted by phone and information may also be collected via medical record review ^ If still on study medication at the time of delivery

[#] if indicated for HIV+ participants

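### Section 9.3 compares V3 ALT/AST with a Screening result that may be up to 18 weeks old at first dose (22 with look-back labs), and no pre-dose hepatic panel is scheduled at V2

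*Protocol*

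**What the plan says.** Section 9.3 lists three criteria for permanent discontinuation that use ALT or AST.

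- Bullet 1: a confirmed "5-fold or greater increase in ALT or AST at the V3 visit compared to baseline result (Screening visit"), with the value also above 3 times ULN and no other cause.
- Bullet 2: "Any increase of ALT or AST above baseline (Screening visit) at the V3 visit" together with new ascites, jaundice or encephalopathy that has no other cause.
- Bullet 3: a confirmed "3-fold or greater increase in ALT or AST accompanied by direct bilirubin >2x the upper limit of normal". It names neither a baseline nor a visit.

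The timing comes from other sections. Screening may take place from 12+0 to 29+6 weeks (section 7.2), and older bloods count towards it: "Routine clinical care laboratory values collected up to 4 weeks prior to the" screening visit date. The hepatic panel carries the look-back asterisk in Table 3. Enrollment is at 20+0 to 30+0 weeks (section 5.2, item 6). Dosing begins at that visit: "Provide study medication and observe first dose (day 1) of medication in office" (Table 4). On the minimum gap, Table 1 notes: "Screening and Enrollment visits are separate visits and therefore should not occur on the same day".

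The V2 laboratory list in Table 4 covers HCV RNA, a sequencing or stored sample, and HIV RNA where applicable. The "Hepatic Function Panel" row of Appendix I is marked at Screening, V3 and V6 only. Sections 5.2 and 7.2 permit the screening bloods to be repeated before enrollment if there is clinical concern. They do not require it, and section 9.3 does not say that a repeat replaces the Screening value.

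**The concern.** A fold-change stopping rule is meant to detect liver injury that arises on the drug. Its denominator should therefore describe the participant just before the first dose. Here it describes her at Screening, and no upper limit is set on the age of the panel beyond what the visit windows imply. Whatever ALT or AST does between Screening and V2 is counted as if it had happened on treatment.

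The error can go either way. A rise before dosing can make a small on-treatment change look like a 5-fold one and open a decision to end a curative course; section 13.3.1 itself notes that an incomplete course may lead to resistance. A fall before dosing can hide a true 5-fold on-treatment rise from the numerical rule. V3 is the only scheduled on-treatment hepatic panel, so the scheduled ALT/AST check rests on this one comparison.

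**Working it through.** The plan states no figure for the age of the baseline, so it is derived from the windows.

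**Age of the Screening panel at first dose** (first dose = V2)

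- Panel drawn at a 12+0 Screening visit, enrolled at 20+0: 20 − 12 = 8 weeks.
- Panel drawn at a 12+0 Screening visit, enrolled at 30+0: 30 − 12 = 18 weeks.
- With the 4-week look-back the draw can be at 12 − 4 = 8+0 weeks. This gives 20 − 8 = 12 weeks and 30 − 8 = 22 weeks.
- Shortest gap between the two visits: 1 day, because they may not share a date.

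**Age at V3** (4 weeks ± 7 days after treatment start, that is +3 to +5 weeks)

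- 18 weeks becomes 21 to 23 weeks.
- 22 weeks becomes 25 to 27 weeks.
- With a panel at V2 before the first dose, it would be 3 to 5 weeks.

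**Effect on the 5-fold rule**

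Let k = pre-dose value / Screening value and f = V3 value / pre-dose value, so that f is the on-drug change. The protocol's ratio is V3 / Screening = k × f. Where the >3 × ULN condition is also met, the rule is reached when k × f = 5, that is at f = 5/k.

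| k (assumed) | On-drug fold at which the rule is reached |
|---|---|
| 0.5 | 5/0.5 = 10 |
| 1 | 5/1 = 5 (as intended) |
| 2 | 5/2 = 2.5 |
| 3 | 5/3 = 1.67 |

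**Two assumed illustrations** (multiples of ULN; the protocol gives no data on ALT variability)

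- Trigger: Screening 1, pre-dose 3, V3 5.5. On the rule 5.5/1 = 5.5-fold, and 5.5 > 3, so the numerical criterion is met. On drug 5.5/3 = 1.83-fold.
- Mask: Screening 2, pre-dose 1, V3 5.5. On the rule 5.5/2 = 2.75-fold, so it is not met. On drug 5.5/1 = 5.5-fold.

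**Bullet 2.** The same mixing occurs, but the criterion needs only some increase and depends mainly on the new hepatic sign, so the baseline matters less. **Bullet 3.** It names no baseline, so there is nothing to compute.

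**The case against.** The strongest case against is that the document is coherent. Section 9.3 names a baseline, the schedule collects it, and nothing is contradicted or miscalculated. A pre-dose panel is better practice, but its absence is a design choice. That stands, and it is why this is a recommended change and not an error that invalidates anything.

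The safeguards are also substantial. Bullet 1 needs a second result, a value above 3 times ULN and the exclusion of other causes. The PSRT is consulted, and the independent safety physician and a hepatologist site investigator review each case before a stop. Section 9 allows stopping in general only where risk outweighs benefit. A masked case can still be caught by the undue-risk criterion, by the rule for related Grade 3 and 4 events (section 9.4) or by interim repeats (section 7.5.1). At enrollment, exclusion 5 is judged again and the history is updated. Repeat bloods or routine-care records may in practice supply a pre-dose value, and the Clinical Management SSP, which is not available here, may add work-up guidance. All of this reduces the consequence. None of it guarantees a pre-dose value or changes the comparator that section 9.3 names, and a confirmatory draw confirms only the V3 value.

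Three stronger readings are tempting, and the documents do not support them.

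- A reader might infer that the baseline's age produces very high thresholds, such as 50 times ULN when Screening is at the 10 times ULN entry limit (5 × 10). That follows from the 5-fold rule and the entry limit; a same-day panel at 10 times ULN would give the same threshold.
- A reader might take "If greater than 30 days between screening and enrollment, HIV RNA PCR must be repeated/available and within eligibility criteria to enroll" (Table 3 footnote) as proof that the protocol should limit the hepatic panel in the same way. That limit serves an eligibility criterion, viral suppression, and not a safety comparator. Other screening safety labs are not repeated at V2 either.
- A reader might infer that wrong stops or missed injuries will be common. The documents give neither the distribution of the gap nor the variability of ALT. The entry criteria (chronic infection or no clinical evidence of acute hepatitis, no cirrhosis, ALT and AST not above 10 times ULN) make large swings less likely, though not impossible.

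**Conclusion.** The point holds. Bullets 1 and 2 of section 9.3 use a comparator that may be up to 18 weeks old at first dose, or 22 with look-back labs. No V2 hepatic panel is scheduled, and a discretionary repeat is not named as the baseline. Change before dosing can therefore trigger or mask the numerical criterion, chiefly the 5-fold rule in bullet 1.

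The 18- and 22-week figures are exact, but they are the extremes that the windows permit, not typical values. The fold examples rest on assumed values, and the frequency of such cases is unknown. The consequence is confined to individual safety stopping. A ratio at V3 opens a reviewed decision and does not stop treatment automatically. The SVR12 and preterm-birth analyses and the sample size are not affected. The change should be made because it is cheap and concerns the only scheduled on-treatment liver check.

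**What to change.** 1. In section 9.3, define baseline as the last ALT/AST result before the first dose, so that any repeat before dosing supersedes the Screening value. Say the same in bullet 3 for consistency.
2. Add a hepatic panel to the existing V2 blood draw, before the observed first dose, at least when the last panel is older than a stated limit such as 30 days. Count the limit from the draw date: counted from the Screening visit, a 30-day limit would still admit a look-back panel 30 + 28 = 58 days old. A panel for everyone at V2 would also remove the remaining gap of up to 30 days; the sponsor may choose.
3. Update Table 4 and Appendix I. Leave the fold thresholds unchanged.

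The cost is a small protocol amendment and one routine laboratory panel for some participants (or all, if the sponsor prefers) on a draw that already takes place. No visit is added. Dosing need not wait for the result, because its use is as the comparator at V3.
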